12.6.4 Physical Examinations, 12-Lead ECGs, and Other Observations Related to Safety

12.6.4.1 Physical Examination

Physical examination results will not be summarized but will be provided in a listing.

### 12.6.4.2 12-Lead ECG

12-lead ECG parameters will be analyzed and transferred externally to PRA. These parameters will be summarized as continuous variables. In addition to summary tables PCS ECG observations will be flagged in data listings based on the criteria given in Table 4.

ECG Parameter	Unit	Low PCS Criteria	High PCS Criteria
Heart rate	bpm	≤50 and decrease of ≥15 from baseline	≥120 and increase of ≥15 from baseline
PR Interval	ms	<120 and baseline value ≥120	>210 and baseline value ≤200
QRS Complex	ms	None	>110 and baseline value ≤110
QTcF	ms	None	Prolongation >30 from baseline

TABLE 4. ECG PCS CRITERIA

#### 12.6.4.3 Pregnancy

#### All pregnancy results will be listed.

### 12.6.4.4 Stanford Sleepiness Scale (SSS)

A summary of SSS will show frequency and percentage of subjects at each rating level, and a plot showing mean (SE) SSS at each applicable study time point will be provided.

### 12.6.4.5 Columbia-Suicide Severity Rating Scale (C-SSRS)

For the 5 suicidal ideation questions ("Wish to be dead," "Non-specific active suicidal thoughts," "Active suicidal ideation with any methods (not plan) without intent to act," "Active suicidal ideation with some intent to act, without specific plan," "Active suicidal ideation with specific plan and intent") and the 5 suicidal behavior questions ("Preparatory acts or behavior," "Aborted attempt," "Interrupted attempt," "Suicide attempt," "Suicide behavior") of the C-SSRS, the number of subjects who answered "yes" will be tabulated for each applicable study time point. Other data collected on the C-SSRS (e.g., ideation intensity measures) will be provided in data listings only.

# 13.0 Validation

Quality control procedures will be documented separately in the study specific quality control plan.

# Appendix 1 Glossary of Abbreviations

Glossary of Abbrevia	ations:
AE	Adverse event
CFB	Change from Baseline
CGI-I	Clinical Global Impression - Improvement
CGI-S	Clinical Global Impression – Severity
CRF	Case Report Form
CSR	Clinical Study Report
C-SSRS	Columbia-Suicide Severity Rating Scale
CTMS	Clinical Trials Management System
DDE	Drug Dictionary Enhanced
DRC	Data Review Committee
ECG	Electrocardiogram
EDPS	Edinburgh Postnatal Depression Scale
FCS	Fully Conditional Specification
GEE	General Estimating Equations
GNX	Ganaxolone
HAMD	Hamilton Depression Rating Scale
HAMD6	Hamilton Depression Rating Scale 6-item version
HAMD17	Hamilton Depression Rating Scale 17-item version
HCG	Human Chorionic Gonadotropin
IP	Investigational Product
IV	Intravenous
IxRS	Interactive Voice and/or Web Response System
MAR	Missing at Random
MCAR	Missing Completely at Random
MedDRA	Medical Dictionary for Regulatory Activitites
MINI	Mini International Neuropsychiatric Interview
mITT	Modified Intention-to-treat
MMRM	Mixed Model Repeated Measures
PBO	Placebo
PCS	Potentially Clinically Significant

PRS 005 T 17 F

Strictly Confidential. © 2004-2015, PRA Health Sciences. All rights reserved.

Page 29 of 35

PK	Pharmacokinetic
PP	Per Protocol
PPD	Postpartum Depression
PT	Preferred Term
Q1/Q3	First Quartile/Third Quartile
SAE	Serious Adverse Event
SAFER	State versus trait; Assessability; Face validity; Ecological Validity; and Rule of 3 Ps
SAP	Statistical Analysis Plan
SD	Standard Deviation
SOC	System Organ Class
SSS	Stanford Sleepiness Scale
STAI6	Spielberger State-Trait Anxiety Inventory 6-item version
TEAE	Treatment-Emergent AE
TFL	Table, figure and listing
TSH	Thyroid Stimulating Hormone
WHO	World Health Organization

# Appendix 2 Adverse Event Start/Stop Date Imputation

Imputation Rules for Partial Dates (D = day, M = month, Y = year)			
Parameter	Missing	Additional Conditions	Imputation
Start date for	D	M and Y same as M and Y of first dose	Date of first dose of study drug
AEs		of study drug	
		M and/or Y not same as date of first	First day of month
		dose of study drug	
	D and M	Y same as Y of first dose of study drug	Date of first dose of study drug
		Y prior to Y of first dose of study drug	Date of screening date
		but same as Y of screening date	
	D, M, Y	None - date completely missing	Date of first dose of study drug
Stop date for	D	M and Y same as M and Y of last dose	Date of last dose of study drug
AEs		of study drug	
		M and/or Y not same as date of last	Use last day of month
		dose of study drug	
	D and M	Y same as Y of last dose of study drug	Date of last dose of study drug
		Y not same as Y of last dose of study	Use Dec 31
		drug	
	D, M, Y	None - date completely missing	No imputation, but assume
			ongoing

Note: In all cases, if an estimated start date is after a complete stop date, use the first day of the stop date month.

Similarly, if the estimated stop date is before a complete or imputed start date, use the last day of the start day month.

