### 7.2 Safety

### 7.2.1 Adverse Events (AE)

An AE is any untoward medical occurrence in a clinical investigation subject administered a pharmaceutical product and that does not necessarily have a causal relationship with this treatment. Data on AEs will be collected at each visit from the time the informed consent is signed until the end of the follow-up period. This includes AEs occurring during the screening phase of the study, regardless of whether or not investigational product has been administered. AEs will be coded using Medical Dictionary for Regulatory Activities (MedDRA) 20.0. Rules for partial dates are provided in Appendix 2.

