#### 12.6.1 Adverse Events

AEs reported from screening through EOS will be coded according to MedDRA® (Medical Dictionary for Regulatory Activities) version 20.0 or greater. Each reported AE will be mapped to a Preferred Term (PT) and a System Organ Class (SOC).

A treatment-emergent AE (TEAE) will be defined as an AE that began or worsened after the first dose of IP and no later than 30 days after the last dose of IP. AEs with insufficient date or time information to determine whether or not they were treatment-emergent will be considered treatment-emergent.

All TEAEs will be listed. In addition, separate listings will be done for non-treatment-emergent AEs and serious AEs (SAEs), treatment-emergent SAEs, and TEAEs that resulted in death, IP discontinuation, IP interruption, or dose reduction. Listings will include reported term, PT, and SOC; start and stop date; whether or not the AE was serious; severity; whether or not the AE was related to IP; action taken; and outcome.

Incidence and number of TEAEs will be summarized by SOC and PTs within SOCs. Summaries will include assessments of severity and relationship to IP. Missing severity will be considered severe and missing relationship will be considered related. Only the most related TEAE per subject for a given PT will be counted in summaries by relationship; similarly, only the most severe TEAE will be counted in summaries by severity. Separate summaries will be done for TEAEs related to IP and TEAEs resulting in IP discontinuation or interruption, or dose reduction. Summaries will be done separately for (a) all TEAEs and (b) treatment-emergent SAEs only.

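### SAP Appendix 2 can make an adverse event recorded as over before the month of first dose treatment-emergent, because its safeguard covers only complete stop dates

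*SAP*

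**What the plan says.** SAP 7.2.1 collects AEs from consent and refers to Appendix 2 for partial dates. On the collection period it adds: "This includes AEs occurring during the screening phase of the study, regardless of whether or not investigational product has been administered".

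In the Appendix 2 table, a start date without day and month is set to the date of first dose when the condition "Y same as Y of first dose of study drug" is met. A start date under "None - date completely missing" is treated the same way. A stop date that lacks only the day, outside the month of last dose, follows "Use last day of month". A stop date giving only a year other than the last-dose year becomes 31 December of that year.

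Two sentences below the table settle conflicts. The first moves the start: "Note: In all cases, if an estimated start date is after a complete stop date, use the first day of the stop date month". The second moves the stop: "Similarly, if the estimated stop date is before a complete or imputed start date, use the last day of the start day month".

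SAP 12.6.1 defines a treatment-emergent AE as one that began or worsened after the first dose and within 30 days of the last, with this default: "AEs with insufficient date or time information to determine whether or not they were treatment-emergent will be considered treatment-emergent".

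**The concern.** The two conflict sentences trust different dates. When the stop date is complete, the recorded stop wins and the imputed start gives way. When the stop date lacks its day or month, the imputed start wins and the recorded stop month or year gives way. Yet the missing day makes no difference when the whole recorded month lies before the first dose: every day in that month is pre-dose, so the recorded information already shows that the AE ended before dosing.

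The rule also sits badly with two other parts of the SAP. The default in 12.6.1 is for dates too incomplete to decide treatment-emergence, and here they are complete enough. For medications, SAP 12.4.3 does the opposite: a partial date that allows a drug to be classed as prior is used to class it so.

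Safety is the first-listed objective and is read from by-arm incidence in small arms. If severity or relationship is also blank, 12.6.1 would carry the same event into the summaries as severe or related.

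**Working it through.** There is no planned figure to reproduce. The check is to apply the Appendix 2 rows and then the two conflict sentences literally. The dates are assumed examples. Unless a row says otherwise, first dose is 10 March 2018 and last dose 12 March 2018 (a 60-hour infusion).

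| Recorded start | Recorded stop | After the table rows | After the conflict sentences | Treatment-emergent? |
|---|---|---|---|---|
| missing, or 2018 | Feb 2018 | 10 Mar / 28 Feb | 10 Mar to 31 Mar 2018 | yes, via the 12.6.1 default |
| missing, or 2018 | 27 Feb 2018 | 10 Mar / 27 Feb | 1 Feb to 27 Feb 2018 | no |
| Feb 2018 | Feb 2018 | 1 Feb / 28 Feb | unchanged | no |
| missing (first dose 10 Jan 2018) | 2017 | 10 Jan 2018 / 31 Dec 2017 | 10 Jan to 31 Jan 2018 | yes, via the default |
| missing (first dose 8 Jan 2019) | Dec 2018 | 8 Jan 2019 / 31 Dec 2018 | 8 Jan to 31 Jan 2019 | yes, via the default |
| 2018 (first dose 8 Jan 2019, screening 27 Dec 2018) | Dec 2018 | 27 Dec / 31 Dec 2018 | unchanged | no |

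Rows 1 and 2 differ only in whether the day of the stop is recorded, and they get opposite classifications. Rows 3 and 6 show the limits: there is no error if the start month is recorded, or if the start year is the year before first dose and equals the screening year.

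The route to treatment-emergent status has two steps. Appendix 2 puts the start on the first-dose date. That date, without a time, is not strictly after the first dose, so the event is counted through the 12.6.1 default for missing time. The second conflict sentence does not cause the classification. Without it the start would still be 10 March and the stop 28 February. What the sentence does is replace the recorded month and so remove the contradiction that would have exposed the problem.

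Can it arise? Screening runs up to 14 days, or 21 with approval (Protocol 7.1). The window reaches the previous calendar month for first doses on days 1 to 14 of a month: 14 × 12 = 168 of 365 dates (46%). With 21 days it is 21 × 12 = 252 of 365 (69%). This shows opportunity, not frequency.

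Size per event: cohorts of about 10 to 30 women randomized 1:1 (SAP 6.1) give arms of about 5 to 15. One extra woman with a preferred term adds 1/15 = 6.7 to 1/5 = 20 percentage points. For Cohort 3, which was to be completed with 20 subjects (Protocol 1.2.1.4), it is about 1/10 = 10 points.

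**The case against.** The strongest objection is that the text does not settle the treatment-emergent classification. Appendix 2 sets dates, 12.6.1 sets status, and a recorded stop month before first dose could be held to be sufficient information, which would leave the default inapplicable. That reading is sensible, and it is what the plan ought to say. But no rule in the SAP lets a partial stop date exclude treatment-emergence, and once the second conflict sentence has run, the derived dates no longer show the pre-dose month. A programmer working from the text would count the event.

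It is also fair that the trigger is remote. It needs a start without a month and a stop without a day. Protocol 8.1.3 collects AE start and stop dates and times, and queries are resolved before lock. This stands and limits the weight of the point, although Protocol 9.4 and SAP 8.3 both name incomplete recall of start and stop dates as a foreseen problem.

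Third, the error runs in the direction the plan has chosen: missing severity counts as severe, missing relationship as related. The rule ignores treatment arm and can only add events. This too stands, but in arms this small a single added event falls in one arm and shifts the comparison.

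A reader might go further and infer that the stop-date rows hide persistence after treatment, because a stop without a day in the last-dose month, or with only the last-dose year, is set to the last-dose date. The documents do not support a change there. SAP 12.6.1 and Appendix 3 plan no summary of AE duration or resolution, and the listings also carry outcome. Nor is month-end imputation clearly more accurate. Take a 30-day month, last dose on day L, and a true stop spread evenly over days L+1 to 30. The current rule shortens the AE by (31 − L)/2 days on average and month-end lengthens it by (29 − L)/2. Averaged over L = 1 to 29 (mean 15), that is 8 days against 7.

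**Conclusion.** The point holds in a narrow form. For an AE whose start is missing or gives only the dosing year, and whose partial stop date lies wholly before the month or year of first dose, Appendix 2 read literally discards the recorded stop and gives a start from which 12.6.1 would count the event as treatment-emergent. The plan handles the same event correctly when the stop date is complete.

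The conclusion rests on a literal reading of Appendix 2 and on the 12.6.1 default being applied to an imputed start with no time. The number of AEs affected cannot be derived from the documents and is probably small. The 46% and 69% above should not be taken as the share of AEs affected, because they say nothing about how often both dates are partial. Each affected event adds about 7 to 20 points to a preferred-term incidence in one arm; none is removed. This is a correction worth making because it is nearly free, not because it threatens the safety conclusions.

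**What to change.** Extend the first conflict sentence in Appendix 2 to partial stop dates. Suggested wording: if the recorded stop month and year, or the stop year alone, is earlier than that of the first dose, the AE is not treatment-emergent, and a start that would otherwise be imputed after it is set to the first day of the recorded stop month (or year). Add that the second conflict sentence may not move a stop date outside its recorded month or year. In 12.6.1, add that such a stop date is sufficient information, so the default does not apply. In the first example the AE would then run from 1 to 28 February 2018 and not be treatment-emergent.

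The second sentence keeps its legitimate use. An AE starting after the last dose, with a stop recorded only as that same month, is still set to the month end. A recorded start later than a recorded stop month is a data contradiction and belongs in a query.

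Leave the rows that use the date of last dose as they are. The cost is a line or two of SAP text and one change to the date derivation, with no new data. SAP 3.0 allows amendment up to unblinding, with sponsor sign-off before programming changes, so it should be in place before the Cohorts 1-3 unblinding described in SAP 10.2.

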# Appendix 3 Tables, Figures, Listings, and Supportive SAS Output Appendices

List of Post-Text Tables, Figures :			
Output	Title	Analysis Set	
Table 14.1.1	Subject Disposition	Randomized	
Table 14.1.2.1	Baseline Characteristics	Safety	
Table 14.1.3.X	Medical History by System Organ Class and Preferred Term	Safety	
Table 14.1.4.X	Prior Medications by WHO Drug Dictionary Preferred Term	Safety	
Table 14.1.5.X	Concomitant Medications by WHO Drug Dictionary Preferred Term	Safety	
Table 14.2.1.1.1.1	Observed Values and Changes From Baseline in HAMD17 Total Score	mITT	
Table 14.2.1.1.2.1	Observed Values and Changes From Baseline in HAMD17 Bech Subscale (HAMD6)	mITT	
Table 14.2.1.1.3.1	Observed Values and Changes From Baseline in HAMD17 Anxiety/Somatization Subscale	mITT	
Table 14.2.1.1.4.1	Observed Values and Changes From Baseline in HAMD17 Gibbons Subscale	mITT	
Table 14.2.1.2.1.1	HAMD17 Total Score Response	mITT	
Table 14.2.1.3.1.1	HAMD17 Total Score Remission	mITT	
Table 14.2.2.1.1.1	Observed Values and Changes From Baseline in EPDS Total Score	mITT	
Table 14.2.2.1.2.1	Observed Values and Changes From Baseline in EPDS Anxiety Subscale		
Table 14.2.3.1.1.1	Observed Values and Changes From Baseline in STAI6 Total Score	mITT	
Table 14.2.4.1.1	CGI-Improvement	mITT	
Table 14.3.1.X	Treatment Exposure (IV/Infusion)	Safety	
Table 14.3.1.3	Treatment Exposures	Safety	
Table 14.3.2.1	Summary of Treatment-Emergent Adverse Events (TEAEs)	Safety	
Table 14.3.2.2.1	Incidence and Number of Treatment-Emergent Adverse Events	Safety	
Table 14.3.2.2.2	Incidence and Number of Treatment-Emergent Adverse Events Related to Investigational Product	Safety	
Table 14.3.2.2.3	Incidence and Number of Treatment-Emergent Adverse Events Resulting in Investigational Product Discontinuation	Safety	
Table 14.3.2.2.4	Incidence and Number of Treatment-Emergent Adverse Events Resulting in Investigational Product Dose Reduction or Interruption	Safety	
Table 14.3.2.2.5	Incidence of Treatment-Emergent Adverse Event Preferred Terms in Order of Descending Incidence Among All Subjects	Safety	
Table 14.3.2.3.1	Incidence and Number of Treatment-Emergent Serious Adverse Events	Safety	

PRS 005 T 17 F

Page 32 of 35

Table 14.3.2.3.2	Incidence and Number of Treatment-Emergent Serious Adverse Events Related to Investigational Product	Safety
Table 14.3.2.3.3	Incidence and Number of Treatment-Emergent Serious Adverse Events Resulting in Investigational Product Discontinuation	Safety
Table 14.3.2.3.4	Incidence and Number of Treatment-Emergent Serious Adverse Events Resulting in Investigational Product Dose Reduction or Interruption	Safety
Table 14.3.2.3.5	Incidence of Treatment-Emergent Serious Adverse Event Preferred Terms in Order of Descending Incidence Among All Subjects	Safety
Table 14.3.3.1.X	Hematology Results by Time Point	Safety
Table 14.3.3.2.X	Biochemistry Results by Time Point	Safety
Table 14.3.3.3.X	Urinalysis Results by Time Point	Safety
Table 14.3.3.4.X	Urine Drug Screen by Time Point	Safety
Table 14.3.4.X	Vital Sign Results by Time Point	Safety
Table 14.3.5.X	Electrocardiogram Results	Safety
Table 14.3.6	Stanford Sleepiness Scale	Safety
Table 14.3.7.X	Columbia-Suicide Severity Rating Scale (C-SSRS) – Suicidal Ideation and Behavior by Time Point	Safety
Figure 14.2.1.1.1.1.1	Mean (SE) HAMD17 Total Score	mITT
Figure 14.2.1.1.1.3.1	Mean (SE) HAMD17 Total Score	mITT
Figure 14.2.1.1.2.1.1	Mean (SE) HAMD17 Bech Subscale (HAMD6)	mITT
Figure 14.2.1.1.2.3.1	Mean (SE) HAMD17 Bech Subscale (HAMD6)	mITT
Figure 14.2.1.1.3.1.1	Mean (SE) HAMD17 Anxiety Subscale	mITT
Figure 14.2.1.1.3.3.1	Mean (SE) HAMD17 Anxiety Subscale	mITT
Figure 14.2.1.1.4.1.1	Mean (SE) HAMD17 Gibbons Subscale	mITT
Figure 14.2.1.1.4.3.1	Mean (SE) HAMD17 Gibbons Subscale	mITT
Figure 14.2.1.1.5.4.1	Mean HAMD17 Individual Items	mITT
Figure 14.2.1.2.1.1	HAMD17 Total Score - Response	mITT
Figure 14.2.1.3.1.1	HAMD17 Total Score - Remission	mITT
Figure 14.2.2.1.1.1.1	Mean (SE) EPDS Total Score	mITT
Figure 14.2.2.1.1.3.1	Mean (SE) EPDS Total Score	mITT
Figure 14.2.2.1.2.1.1	Mean (SE) EPDS Anxiety Subscale	mITT
Figure 14.2.2.1.2.3.1	Mean (SE) EPDS Anxiety Subscale	mITT
Figure 14.2.2.1.3.4.1	Mean EPDS Individual Items	mITT
Figure 14.2.3.1.1.1.1	Mean (SE) STAI6 Total Score	mITT
Figure 14.2.3.1.1.3.1	Mean (SE) STAI6 Total Score	mITT
Figure 14.2.3.1.2.4.1	Mean STAI6 Individual Items	mITT

PRS 005 T 17 F

Page 33 of 35

Figure 14.2.4.1.1.1	CGI-Improvement	mITT
Figure 14.2.4.2.3.1	CGI-Improvement	mITT
Figure 14.3.6	Stanford Sleepiness Scale	Safety

List of End of Text Listings:			
Output	Title	Analysis Set	
Listing 16.1.7.X	Randomization Assignments	Screened	
Listing 16.2.1	Subject Disposition	Randomized	
Listing 16.2.2.X	Protocol Deviations	Randomized	
Listing 16.2.3.X	Subject Analysis Sets	Randomized	
Listing 16.2.4.1	Baseline Characteristics	Randomized	
Listing 16.2.4.2.X	Medical History	Safety	
Listing 16.2.4.3.X	Prior and Concomitant Medications	Safety	
Listing 16.2.4.4.X	Mini International Neuropsychiatric Interview (MINI)	Safety	
Listing 16.2.4.5.X	SAFER Interview	Safety	
Listing 16.2.5.1.X	Study Drug Administration (IV/Infusion)	Safety	
Listing 16.2.5.2.X	Study Drug Interruption (IV/Infusion)	Safety	
Listing 16.2.5.3.3	Study Drug Administration (Bolus)	Safety	
Listing 16.2.6.1	Hamilton Depression Rating Scale 17-Item Version (HAMD17)	Randomized	
Listing 16.2.6.2	Edinburgh Postnatal Depression Scale (EPDS)	Randomized	
Listing 16.2.6.3	Spielberg Trait-State Anxiety Inventory 6-Item Version (STAI6)	Randomized	
Listing 16.2.6.4	Clinical Global Impression – Improvement (CGI-I)	Randomized	
Listing 16.2.6.5	Obsessive Thoughts	Randomized	
Listing 16.2.7.1	Treatment-Emergent Adverse Events	Safety	
Listing 16.2.7.2	Treatment-Emergent Serious Adverse Events	Safety	
Listing 16.2.7.3	Treatment Emergent Adverse Events Resulting in IP Discontinuation	Safety	
Listing 16.2.7.4	Treatment Emergent Adverse Events Resulting in IP Dose Reduction or Interruption	Safety	
Listing 16.2.7.5	Treatment-Emergent Adverse Events Resulting in Death	Safety	
Listing 16.2.7.6.1	Non-Treatment-Emergent Adverse Events	Screened	
Listing 16.2.7.6.2	Non-Treatment-Emergent Serious Adverse Events	Screened	
Listing 16.2.8.1.X	Hematology Results (Quantitative Parameters)	Safety	
Listing 16.2.8.2.X	Biochemistry Results (Quantitative Parameters)	Safety	

PRS 005 T 17 F

PRAHEALTHSCIENCES

Listing 16.2.8.3.X	Urinalysis Results (Quantitative Parameters)	Safety
Listing 16.2.8.4.X	Clinical Laboratory Results (Semi-Quantitative and Qualitative Parameters)	Safety
Listing 16.2.8.5.X	Urine Pregnancy Test Results	Safety
Listing 16.2.9.X	Vital Signs	Safety
Listing 16.2.10.1.X	Electrocardiogram Results Part 1	Safety
Listing 16.2.10.2.X	Electrocardiogram Results Part 2	Safety
Listing 16.2.11.X	Physical Examinations	Safety
Listing 16.2.12	Stanford Sleepiness Scale	Safety
Listing 16.2.13.X	Columbia-Suicide Severity Rating Scale (C-SSRS)	Safety
